4. STUDY ENDPOINTS/OUTCOMES

The co-primary endpoints of this study are:

1. Mean percent change from screening/baseline to week 12 in the inflammatory (papules and pustules) lesion counts;
2. Mean percent change from screening/baseline to week 12 in the non-inflammatory (open and closed comedones) lesion counts.

5. HYPOTHESES TESTING

Hypothesis of Equivalence

A two-sided, 90% confidence intervals on the test/reference ratio for mean percent change from Baseline in the inflammatory and non-inflammatory lesion counts will be constructed using Fieller's method. The estimates of treatment means and standard errors will be obtained from a two-way Analysis of Variance (ANOVA) of the Test and Reference results, using a statistical model containing terms for treatment and center. Non-parametric methods will be considered if the skewness factor for the residuals from the ANOVA model is outside the range -2 to +2.

Bioequivalence will be established if the 90% confidence intervals for the ratios of test/reference means for both the inflammatory and non-inflammatory lesions are contained within the interval [0.80, 1.25].

Hypothesis of Superiority

The null hypothesis to be tested is that there is no difference in the mean percent change (reduction) from baseline in the inflammatory and non-inflammatory lesion counts between the active treatment and the Vehicle treatment. The hypothesis testing will be performed separately for the Test treatment versus the Vehicle treatment and for the Reference treatment versus the Vehicle treatment using ANOVA under assumption of normal error and homogeneity of variance. Only data for the relevant two treatment arms will be included in each ANOVA. Similarly to bioequivalence, non-parametric methods will be considered if the skewness factor for the residuals from the ANOVA model is outside the range -2 to +2.

Superiority will be established if the mean percent change (reduction) from Baseline in both the inflammatory and non-inflammatory lesion count for each active treatment is greater than, and statistically different from ($p < 0.05$, two-sided), that for the Vehicle.

6. ANALYSIS SUBSETS

6.1 Safety Population

The safety population will include all randomized subjects who use at least one dose of product (as recorded at the “Investigational Medicinal Product Use Compliance” CRF based on the subject diary).

The Safety population will be the primary population for the safety analysis. Subjects will be analyzed according to the treatment they actually received.

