Subjects who withdraw from the study early will have Early Discontinuation procedures performed. Subjects who withdraw from the study will not be replaced. All subjects who are randomized will be included in the safety monitoring tabulating all adverse events experienced after dosing.

A significant or major protocol deviation is defined as any subject or Investigator activity that could have possibly interfered with the therapeutic administration of the treatment, safety or well-being of the subject or the precise evaluation of treatment efficacy such as may affect data integrity. Subjects with protocol deviations are not required to be discontinued from the study unless, in the Investigator's opinion, continuation in the study could be harmful to the health or wellbeing of the subject. Subjects that have a major protocol deviation which effects their safety or wellbeing should be discontinued.

The reasons for a Subject discontinuation will be documented. If a Subject is discontinued from the study for any reason, Early Discontinuation Visit procedures will be completed and any outstanding data and study drug should be collected if possible. In addition to the reason for discontinuation the collected data will include the initiation of any rescue medicines, the date of removal and will be documented in the electronic Case Report Form (eCRF). The Sponsor will be notified.

Before a subject is considered to be lost to follow-up, the Principal Investigator will document all attempts to reach the Subject twice by telephone and will send a certified follow-up letter.

In the event that a subject discontinues from the study at any time due to an adverse event (AE), the reason for discontinuation, the nature of the event and its clinical course must be fully documented (see also reporting AEs and SAES, Section 11.0). For such a subject, the Principal Investigator must strive to follow the subject until the adverse event has resolved, becomes clinically insignificant, is stabilized or the subject is lost to follow-up. In case of any serious adverse events, procedures for reporting must be followed.

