8.2 Visit 2: First Interim (Week 4; Day 28 [redacted] Days)

The following procedures will be performed at Visit 2:

1. **Initial Check:** Temperature check and COVID-19 symptom screening.
2. **Pregnancy Test:** A urine pregnancy test will be conducted for all females of childbearing potential.
3. **Subject Compliance:** The Subject's compliance with the study protocol, including use, application and compliance of IMP, will be assessed. The Subject's diary will be collected and reviewed for completion.
4. **Investigational Medicinal Product:** The Subject's IMP dispensed at Visit 1 will be returned to the Independent Dispenser for review and re-dispensed if IMP remains.
5. **Concomitant Medication:** The use of concomitant medications since the previous study visit will be documented and assessed for each Subject.
6. **Adverse Events:** The occurrence of all AEs will be assessed and documented following procedures.
7. **Investigator Global Assessment:** The overall status of the Subject's facial acne vulgaris (from the jaw line to the hairline) will be assessed using the IGA by the Investigator or qualified staff member.
8. **Lesion Count:** Lesion counts will be done by counting the number of facial open and closed comedones, pustules, papules and nodulo-cystic lesions from the jaw line to the hairline. All lesions will be counted, including those present on the nose.
9. **Application Site Reaction:** Subjects will be evaluated for any signs and symptoms such as erythema, dryness, burning/stinging, erosion, edema, pain and itching.

10. Investigational Medicinal Product and Supplies:

The following will be dispensed during Visit 2:

- The investigational product (1 pump) (new pump assigned through the randomization system and or pump from screening/baseline visit re-dispensed if sufficient IMP remains)

- [redacted]
- [redacted]
- [redacted]

It is not anticipated that Subjects will require additional supplies during this visit; additional supplies will be dispensed if required.

- 
-
11. Study instructions will be reviewed with the Subject, including the procedure for application of the IMP.
 12. **Visit 3** (Day 56  days from the date of Visit 1): will be scheduled and the Subject will be instructed to bring all IMP (used, unused, and partially used) and the Subject diary with him or her to this visit. Subjects will be reminded not to use any facial topical products within 12 hours prior to the next scheduled clinic visit.

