8.7 Early Termination of a Subject

A subject may terminate from the study early for any reason at any time without any disadvantages. In this case, the Investigator should make every effort to have the subject return to the next scheduled visit to perform all required Early Termination (Early Discontinuation) visit activities and to collect and reconcile all study IMP. If the subject does not return for the Early Termination (Early Discontinuation) visit, the site should fully document the reason for early termination. All data, including the date and primary reason for termination, must be recorded on the Early Termination (Early Discontinuation) case report form (CRF), and source document.

Any subject who experiences an adverse event may be terminated from the study or from study treatment at any time at the discretion of the Investigator. In this case, the subject should be followed at the discretion of the Investigator until the resolution or stabilization of the AE. All applicable data should be recorded in the adverse events section of the case report form (CRF). If a subject terminates from the study early for multiple reasons that include adverse events, the Early Termination (Early Discontinuation) case report form should indicate that early termination was related to an adverse event.

An exception to this requirement will be the occurrence of an adverse event that in the opinion of the investigator is not severe enough to warrant early termination but that requires the use of a prohibited medication, thereby requiring discontinuation of the subject. In such a case, the reason for discontinuation would be needed to take a prohibited medication, not the adverse event.

The Investigator must inform the Medical Monitor and CRO as soon as possible of all subjects who are being considered for early termination due to adverse events. Additional reports must be provided when requested. The CRO will inform the Sponsor of this event.

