9.5 Assessment of Compliance

Compliance with scheduled application of IMP will be determined from the Subject’s diary. The

Subject will be instructed to use the diary to document all doses taken by checking the yes or no box for the appropriate date. In addition, Subjects will be instructed to document all concomitant medication and AEs on the diary. Used IMP will be returned to the study site at each scheduled visit or Early Discontinuation Visit or as applicable. If the subject does not return the Diary, compliance cannot be determined.

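### SAP 6.1 accepts only a diary-based CRF entry as evidence of dosing, so a treated subject lost before returning any diary could drop out of the adverse event summaries

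*SAP*

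**What the plan says.** SAP 6.1 opens with "The safety population will include all randomized subjects who use at least one dose of product" and then says how use is established: it must be recorded on the product-use compliance "CRF based on the subject diary". No alternative source is named in the readable text.

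Protocol 9.5 takes compliance from the same source ("Compliance with scheduled application of IMP will be determined from the" subject's diary) and adds: "If the subject does not return the Diary, compliance cannot be determined".

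Protocol 5.1.5 words the safety tabulation differently: "All subjects who are randomized will be included in the safety monitoring tabulating all adverse events experienced after dosing". It sets no diary condition.

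Protocol 10.3.2 places the safety analyses on the safety population, and SAP 6.1 calls it the primary population for them. SAP 8 declares one change from the protocol's analyses, to the mITT definition. The protocol's formal definitions of the three populations, in 10.2, are redacted.

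**The concern.** Whether a subject was exposed and whether a diary came back are different questions, and SAP 6.1 makes the first depend on the second. The protocol foresees subjects for whom the answers differ. Subjects dose at home and are told to call the site about severe intolerability. At discontinuation, "any outstanding data and study drug should be collected if possible", and 8.7 provides for subjects who never attend the discontinuation visit.

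The subject at risk of omission uses the cream, reacts, telephones, stops and is not seen again. Under protocol 6.3, irritation that leads to discontinuation is recorded as an adverse event, so this subject may have a known event. If early loss is related to tolerability, leaving such subjects out would tend to lower the reported rates. Comparing safety across the three arms is an objective in protocol section 2.

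**Working it through.** The plan gives no figure to reproduce, and sample size and dropout assumptions are redacted. The check is a reading of the sections together.

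1. **Entry rule.** SAP 6.1 needs a dose recorded on a CRF that is based on the diary.
2. **When the diary first comes back.** Visit 2 is the first scheduled point at which the "diary will be collected and reviewed for completion". A subject whose diary from that visit shows a dose stays in the safety population whatever happens later. The gap therefore mainly concerns subjects lost before Visit 2.
3. **Whether loss without a diary is foreseen.** It is. Protocol 5.1.5 asks for collection only where possible. The visit schedule marks diary collection at unscheduled or early discontinuation visits as needed. Protocol 8.7 says: "If the subject does not return for the Early Termination (Early Discontinuation) visit, the site should fully document the reason for early termination".
4. **Consequence, read literally.** With no diary there is no diary-based dose record, so the subject fails SAP 6.1 and leaves the TEAE summaries of SAP 7.7.1, their denominators and the Fisher comparisons of Test with Reference.
5. **What still shows the subject.** The by-subject listing in SAP 7.7.1 covers all adverse events noted in the study. SAP 7.2 bases disposition percentages on randomized subjects and summarizes exclusions from each population by reason. The irritation shift tables in SAP 7.7.4 use only subjects scored at baseline and at the visit concerned, so someone lost before Visit 2 with no later score would not be counted there in any case.
6. **Comparison with protocol 5.1.5.** That sentence would tabulate this subject's post-dose events; SAP 6.1 would not.

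**Illustration of direction and size (all inputs assumed).** Take 400 subjects in an arm, of whom 16 stop for an adverse event, a true rate of 16/400 = 4.0%. Let *p* be the share of these 16 with no diary and *q* the share of the other 384. The reported rate is 16(1 − *p*) / [400 − 16*p* − 384*q*].

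| *p* | *q* | Reported rate |
|---|---|---|
| 50% | 0% | 8/392 = 2.0% |
| 10% | 0% | 14.4/398.4 = 3.6% |
| 10% | 10% | 14.4/360 = 4.0% |
| 0% | 10% | 16/361.6 = 4.4% |

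Understatement needs diary loss to be more common among subjects with events. Equal loss leaves the rate unchanged, and the reverse pattern raises it. The documents give neither *p* nor *q*.

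**The case against.** The strongest reply is that the exclusion is inferred and not stated. Protocol 13.4 lists drug start and stop dates and relevant telephone conversations as source data, separately from the diary. Protocol 6.3 sends dose modifications to a medication log and dosing eCRF as well as to the diary, including decisions made by documented telephone contact. Protocol 11.1 has the action taken on study drug recorded for each adverse event. The telephone case would thus leave a trace, and nothing says the compliance CRF must stay blank. Protocol 9.5 concerns compliance with the schedule, which is not the same as whether any dose was used. Part of SAP 7.7.5 is redacted and may deal with missing diaries.

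All of this stands as a limit on certainty. It does not remove the point: the sentence that defines the population names only the diary-based record, and the existence of other records makes the remedy easy.

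Three stronger readings should be resisted.

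- A reader might infer that the SAP breaks a protocol rule to put every randomized subject in the safety population. Protocol 5.1.5 is a tabulation rule, itself tied to dosing, and the definitions in 10.2 cannot be read. SAP 8 is compatible with a redacted definition that matches SAP 6.1.
- A reader might infer that discontinuation rates are understated generally. Disposition uses randomized subjects, so only the TEAE-leading-to-discontinuation tables are exposed.
- A reader might infer a distortion between active and vehicle arms. That is possible, but no differential diary loss is shown, and the planned test compares Test with Reference, whose reactions protocol 11.1 expects to be similar.

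**Conclusion.** The point holds in a limited form. SAP 6.1 states an evidence rule that, taken literally and with no visible fallback, can remove an exposed subject with a known adverse event from the safety summaries and tests. The difference from protocol 5.1.5 lies in the diary condition; the one-dose requirement is not shown to conflict with the protocol.

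The size cannot be estimated. It depends on how many subjects are lost before a first diary return and on how sites complete the compliance CRF for them, and the number may be small. The illustrative rates rest wholly on assumed inputs, so a halved adverse event rate should not be read as an expected effect. The exclusions would be visible in the listing, the disposition table and the exclusion summary, but that visibility does not correct the tabulated rates. The co-primary lesion-count analyses use other populations and are outside this point. The wording deserves correction because the remedy is simple.

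**What to change.** In SAP 6.1, define the safety population as all randomized subjects with any documented evidence of at least one use: diary, source record of drug start, telephone contact, adverse event record with action taken on study drug, or a returned used pump.

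Where the first-use date is unknown, use the dispensing date. TEAE status and relative days both need a start date, and protocol 8.1 instructs the first application in the evening, so the dispensing date is a reasonable stand-in. It may classify a few events from earlier that day as treatment-emergent, which errs on the cautious side.

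Reconcile the sentence with protocol 5.1.5, and settle membership before unblinding.

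Optionally, add a sensitivity summary that also includes subjects who were dispensed drug and whose non-use is not confirmed. Its drawback is that a few subjects with no safety data enter the denominator and dilute the rates, which is why it should not replace the main definition.

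The cost is a short SAP revision and a programmed check of non-diary sources for subjects with no diary.

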6.2 Modified Intent to Treat Population (mITT Population)

[REDACTED]

■ [REDACTED]

■ [REDACTED]

■ [REDACTED]

■ [REDACTED]

This population will be considered as supportive for testing the clinical equivalence and as definitive while testing the superiority. Subjects will be analyzed according to the treatment they were randomized to receive.

6.3 Per Protocol Population (PP Population)

[REDACTED]

- [REDACTED]
- [REDACTED]
- [REDACTED]
- [REDACTED]
- [REDACTED]
- [REDACTED]

Subjects who are discontinued early from the study due to lack of treatment [REDACTED] will be included in the PP population as treatment failures (i.e., non-responders) even if they do not have Week 12 evaluation within the visit window or at all. A “last observation carried forward” (LOCF) approach will be used for imputing missing lesion counts in these PP subjects.

Per protocol, subjects whose condition or symptoms worsens and require alternate or supplemental or rescue therapy for the treatment of their condition during the treatment phase of the study should be discontinued, included in the mITT and PP population analysis using LOCF, and provided with effective treatment. The reason for study discontinuation for these subjects should be set to “Lack of treatment effect”, therefore for practical purposes this group of subjects is a subgroup of subjects who are discontinued early from the study due to lack of treatment effect.

[REDACTED]

The PP population will be considered as definitive for testing the clinical equivalence and as supportive while testing the superiority. Subjects will be analyzed according to the treatment they were randomized to receive.

7. STATISTICAL METHODS OF ANALYSIS

7.1 General Principles

All tables, figures, and listings will be produced in the landscape format.

In general, all data will be listed by treatment group, subject and visit where appropriate. The summary tables will also be stratified by, or have columns corresponding to, treatment group.

The total number of subjects in the treatment group (N) under the stated population will be displayed in the header of summary tables.

Data will be summarized using descriptive statistics for continuous variables. Unless otherwise specified, descriptive statistics will include number of subjects, mean, standard deviation, minimum, median, and maximum. The minimum and maximum statistics will be presented to the same number of decimal places as the original data. The mean and median will be presented to one more decimal place than the original data. The standard deviation will be presented to two more decimal places than the original data. The number of missing observations will be presented only if non-zero.

In summary tables of categorical variables counts and percentages will be used. The count [n] indicates the actual number of subjects in a particular category, which should always be less than or equal to the total number of subjects in the respective treatment group/population with known (non-missing) category [N]. Percentage will be obtained by: $\% = n/N*100$. Unless otherwise specified, all percentages will be expressed to one decimal place.

All statistical tests will be two-sided at a significance level of $\alpha = 0.05$, unless otherwise specified. No adjustment will be made for multiplicity.

Relative days will be calculated relative to the date of the first dose of study medication. Relative days will be calculated as follows only when the full assessment date is known (i.e., partial dates will have missing relative days).

For assessment on or after the day of the first dose of study drug:

Relative Day = Date of Assessment – Date of the First Dose of study Drug+1.

For assessment before the day of the first dose of study drug:

Relative Day = Date of Assessment – Date of the First Dose of study Drug.

All dates will be displayed in DDMMYYYY format.

7.2 Subject Disposition

The number of subjects enrolled in the study, randomized to treatment, included in the Safety, mITT and PP populations, prematurely discontinued from the study (along with the reasons for discontinuation) will be calculated. The percentages will be based on the number of subjects randomized to each treatment group. Percentages for discontinuation reasons will be based on the sub-population of subjects who discontinued from the study.

Number and percentage of subjects enrolled by site will be tabulated for all enrolled subjects, Safety, mITT, and PP populations.

Number and percentage of subjects excluded from each of the study populations will be summarized by reason for exclusion.

Details of subject eligibility, informed consent and disposition will be listed.

7.3 Demographic and Baseline Characteristics

Demographic characteristics will include:

- age;
- gender;
- race;
- ethnicity;

Baseline characteristics include:

- Time since acne vulgaris diagnosis (years)

- Baseline inflammatory lesion count (i.e papules and pustules)
- Baseline non-inflammatory lesion count (i.e. open and closed comedones)
- Baseline nodulocystic count (i.e. nodules and cysts)
- Baseline IGA score
- Baseline height, weight and body mass index (BMI)

Descriptive statistics will be presented for age (years), height, weight, BMI, time since diagnosis (years) and lesion counts. Frequency counts and percentages will be presented for race, ethnicity and IGA. Height will be reported in centimeters and weight in kilograms.

Age will be derived from Informed Consent Signed Date and Date of Birth as the number of whole years between those two dates.

Demographic and baseline characteristics will be evaluated for comparability across treatment groups in the following manner. Continuous variables will be analyzed with an ANOVA with factors of treatment and investigational site. Overall p-value for the global null hypothesis of all groups being equal will be displayed. Categorical variables will be analyzed with a Cochran-Mantel-Haenszel stratified by investigational site. For IGA score “row mean scores differ” CMH statistic will be used, while for all other parameters “general association” CMH statistic will be used.

These analyses will be performed for Safety, mITT, and PP populations.

All demographic and baseline characteristics will be listed.

